**Corporate Confidential Information**

**Corporate Confidential Information**

### Corporate Confidential Information

## 9 Safety monitoring

[figure not shown]
In this trial, safety monitoring will be done for

- (1) the 7T MRI exploratory device
- (2) the investigational drug LNA043 and its placebo

by reporting:

- **Device related events:** Adverse device effects and serious adverse device effects, device deficiency that might lead to a SADE, and new findings/updates to already reported events for the device
- **Not device related events:** Adverse events and serious adverse events (which may or may not be related to the investigational drug)

Device related cases (such as device malfunction, device deficiency, procedural errors, device deterioration, inaccurate instructions, degradation or destruction of the device) not meeting the definition of an adverse event are not considered ADE and will not be collected.

**Figure 9-1 Safety monitoring**

## 9.1 Adverse events and Adverse device effects

### 9.1.1 Adverse events

An adverse event (AE) is any untoward medical occurrence (i.e., any unfavorable and unintended sign [including abnormal laboratory findings], symptom or disease) in a subject or clinical investigation subject after providing written informed consent for participation in the study until the end of study visit. Therefore, an AE may or may not be temporally or causally associated with the use of a medicinal (investigational) product.

In addition, all reports of intentional misuse and abuse of the study treatment are also considered an adverse event irrespective if a clinical event has occurred. See [Section 9.6](#) for an overview of the reporting requirements.

The occurrence of adverse events must be sought by non-directive questioning of the subject at each visit during the study. Adverse events also may be detected when they are volunteered by the subject during or between visits or through physical examination finding, laboratory test finding, or other assessments.

Abnormal laboratory values or test results constitute adverse events only if they fulfill at least one of the following criteria:

- they induce clinical signs or symptoms,
- they are considered clinically significant,
- they require therapy.

Clinically significant abnormal laboratory values or test results should be identified through a review of values outside of normal ranges/clinically notable ranges, significant changes from baseline or the previous visit, or values which are considered to be non-typical in patients with underlying disease. Investigators have the responsibility for managing the safety of individual subject and identifying adverse events. Alert ranges for liver and kidney related events are included in [Appendix 1](#) and [Appendix 2](#), respectively.

Adverse events must be recorded on the Adverse Events CRF under the signs, symptoms or diagnosis associated with them, and accompanied by the following information:

1. the Common Toxicity Criteria (CTC) AE grade (version 4.03)

If CTC-AE grading does not exist for an adverse event, use:

- 1 = mild,
- 2 = moderate,
- 3 = severe
- 4 = life threatening\* (see [Section 9.3.1](#) for definition of a serious adverse event (SAE))

\*Note: There may be cases where a CTCAE with a grade of 4 (life-threatening) may not necessarily be an SAE (e.g. certain laboratory abnormalities in the absence of meeting other seriousness criteria).

- CTC-AE grade 5 (death) is not used, but is collected as a seriousness criteria and also collected in other CRFs (e.g. Study Completion, Death/Survival).

2. its relationship to the study treatment

- Yes or No

3. its duration (start and end dates) or if the event is ongoing an outcome of not recovered/not resolved must be reported.

4. whether it constitutes a SAE (see [Section 9.3.1](#) for definition of SAE) and which seriousness criteria have been met

5. Action taken regarding investigational treatment.

All adverse events must be treated appropriately. Treatment may include one or more of the following:

- no action taken (e.g. further observation only)
- investigational treatment dosage increased/reduced
- investigational treatment interrupted/withdrawn
- concomitant medication or non-drug therapy given
- hospitalization/prolonged hospitalization (see [Section 9.3.1](#) for definition of SAE)

6. its outcome (not recovered/not resolved; recovered/resolved; recovering/resolving, recovered/resolved with sequelae; fatal; or unknown).

Information about common side effects already known about the investigational drug can be found in the Investigator's Brochure (IB). Once an adverse event is detected, it must be followed until its resolution or until it is judged to be permanent, and assessment should be made at each visit (or more frequently, if necessary) of any changes in severity, the suspected relationship to the investigational drug, the interventions required to treat it, and the outcome.

The investigator must also instruct each subject to report any new adverse event (beyond the protocol observation period) that the subject, or the subject's personal physician, believes might reasonably be related to study treatment. This information must be recorded in the investigator's source documents; however, if the AE meets the criteria of an SAE, it must be reported to Novartis.

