**Corporate Confidential Information**

[figure not shown]
At Week 12 (Day 85 +/- 5) patients will return to the hospital for regular medical checks and safety evaluations as detailed in the [Assessment Schedule](#). The MRI assessment can be performed either the day of the visit or +/- 3 days from the visit as detailed in the [Assessment Schedule](#).

At Week 28 (Day 197 +/- 7), patients will return for an EoS visit. EoS visit assessments will include safety, **CCI** and other assessments as detailed in the [Assessment Schedule](#).

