## Corporate Confidential Information

-  This is used as baseline MRI
-  MRI can be performed either the same day of surgery, in this case MRI has to be performed before it, or up to three days before Day 29 .
-  MRI assessment can be performed either the same day of the visit or  $\pm 3$  days from the visit
-  MRI assessment can be performed either the same day of visit or  $\pm 7$  days from the visit
-  X-rays will be performed at screening in case the patient doesn't have previous examinations
-  Drug will be administered at the end of the surgery
-  To check if there is SAE 30 days post EOS.

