## **9.2 Adverse device effects**

An adverse device effect (ADE) is an adverse event related to the use of a device. In this study, an ADE refers to the 7T MRI. This includes any adverse event resulting from insufficiencies or inadequacies in the instructions for use, the deployment, the implantation, the installation, the operation, or any malfunction of the device(s). This includes also any event that is a result of a use error or intentional misuse.

The occurrence of adverse device effects should be sought by non-directive questioning of the subject at each visit during the study. Adverse device effects also may be detected when they are volunteered by the subject during or between visits.

Adverse device effects must be recorded on the Adverse Event eCRF page under the signs, symptoms or diagnosis associated with them, accompanied by the following information:

1. the severity grade:
  - 1 (mild): usually transient in nature and generally not interfering with normal activities
  - 2 (moderate): sufficiently discomforting to interfere with normal activities
  - 3 (severe): prevents normal activities
2. its relationship to the device(s) in the comment section
3. its duration (start and end dates or if the event is ongoing an outcome of not recovered/not resolved must be reported)
4. if it constitutes a serious adverse device effect (SADE) the SADE Report Form in paper has to be completed

Once an adverse device effect is detected, it should be followed until its resolution or until it is judged to be permanent, and assessment should be made at each visit (or more frequently, if necessary) of any changes in severity, the suspected relationship to the medicinal product or device(s), the interventions required to treat it, and the outcome.

Information about known side effects of the device(s) can be found in the Informed Consent form. This information will be included in the subject's informed consent and should be discussed with the subject during the study as needed.

The Investigator should also instruct each subject to report any new adverse event/adverse device effect (beyond the protocol observation period) that the subject, or the subject's personal physician, believes might reasonably be related to the device used. This information should be recorded in the Investigator's source documents; however, if the ADE meets the criteria of an SADE, it must be reported to Novartis.

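### AE and device-effect collection closes at the end-of-study visit, but the final 7T MRI may follow that visit by up to 7 days, leaving non-serious effects of such a scan no stated route to the eCRF

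*Protocol*

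**What the plan says.** **Object of monitoring.** Protocol Section 9 lists two objects of safety monitoring. The first is "the 7T MRI exploratory device"; the second is the investigational drug and its placebo.

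**Collection window.** Section 9.1.1 defines an AE as an untoward occurrence "after providing written informed consent for participation in the study until the end of study visit". Section 9.2 states: "An adverse device effect (ADE) is an adverse event related to the use of a device". It sets no separate start or end for ADEs.

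**How ADEs are found and recorded.** Under Section 9.2, ADEs are sought by open questioning at each study visit, may also be volunteered during or between visits, and go on the Adverse Event eCRF page. For effects arising after the observation period, the subject is to be told to report any that might be related to the device. Of these reports the section says: "This information should be recorded in the Investigator's source documents". Only those meeting the criteria for a serious adverse device effect (SADE) must go to the sponsor.

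**Timing of the last visit and scan.** Section 3.1 says: "At Week 28 (Day 197 +/- 7), patients will return for an EoS visit". Footnote 17 of Table 8-1 begins "MRI assessment can be performed either the same day of visit or" and goes on to allow 7 days either side of the visit.

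**After the last visit.** Section 7.1 plans a safety call 30 days later, with its information kept as source documentation. Footnote 20 of Table 8-1 gives the purpose as "To check if there is SAE 30 days post EOS". Section 9.3.2 requires SAE reporting up to 30 days after the last study visit.

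**The concern.** Each rule is reasonable alone, but together they do not fit. The end-of-study (EOS) visit closes AE collection, while a protocol-required exposure to the exploratory device may still lie ahead. Section 9.2 grades ADEs from mild upwards, so the protocol means to collect non-serious effects, and Section 3.7.1 discusses radiofrequency heating as a hazard for some patients. Nothing explains why non-serious effects of a late final scan should be handled differently from those of the first three scans.

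At stake is the completeness of the non-serious device-safety record for the last scan. No efficacy endpoint, sample size or serious-event reporting is affected.

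**Working it through.** There is no planned figure to reproduce. The check is a cross-reading of the protocol and some day arithmetic.

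**1. Which scan footnote 17 governs.** Section 3.1 places scans at Day 3, Week 4, Week 12 and Week 28. In Table 8-1, footnote 14 marks the baseline scan (Day 3). Footnote 15 ties the MRI to surgery and Day 29 (Week 4). Footnote 16 gives 3 days either side, which is the Week 12 window in Section 3.1. Footnote 17, with 7 days either side, is left for Week 28. This is an inference, because the MRI row is not shown.

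**2. Windows in study days.**
- EOS visit: 197 − 7 = Day 190 to 197 + 7 = Day 204.
- Week 28 scan: 190 − 7 = Day 183 to 204 + 7 = Day 211.
- Largest interval by which the scan can follow the visit: 7 days (for example, visit on Day 204 and scan on Day 211).
- Safety call 30 days after the EOS visit: 190 + 30 = Day 220 to 204 + 30 = Day 234.
- Time from a scan done 0 to 7 days after the visit to the call: 30 − 7 = 23 to 30 − 0 = 30 days.

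**3. Whether a later visit asks about each scan.**

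| Scan | Latest day in its stated window | Next scheduled visit that asks about ADEs |
|---|---|---|
| Baseline | Day 3 + 1 = Day 4 | Week 1, from Day 8 − 1 = Day 7 |
| Week 4 | Day 29 | Week 12, from Day 85 − 5 = Day 80 |
| Week 12 | Day 85 + 5 + 3 = Day 93 | EOS, from Day 190 |
| Week 28, before the EOS visit | 1 day before the visit | the EOS visit itself |
| Week 28, 1 to 7 days after the EOS visit | Day 211 | none; only the call, whose stated purpose is SAEs |

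Only the last row lacks a later scheduled visit.

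**4. Where an event from that last row goes.** A non-serious effect falls after the end point in Section 9.1.1, so read literally it is neither an AE nor an ADE. Section 9.2 still has the subject report it, and it is kept in source documents. No step takes it from there to the eCRF, and hence none takes it to the AE tables in Protocol Section 11.4.4.4 or SAP Section 7.2. A serious effect follows Sections 9.3.2 and 9.3.3.2 as before.

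**5. Size.** There are four scans per patient, of which one is final: 1/4 = 25%. The share of scans affected therefore lies between 0 (every final scan on or before the visit) and 25% (every final scan after it). The documents give no distribution of scan days that would narrow this range.

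**The case against.** The strongest reply is that the documents can be read with no gap. Section 3.1 labels the scan as Week 28 (EOS), and a required scan inside its permitted window is naturally part of the observation period. On that view the source-document route in Section 9.2 is not engaged, and the instruction to record ADEs on the eCRF, which carries no end date of its own, still applies. This has force as a statement of likely intent. It does not remove the conflict, because footnote 17 treats the MRI day and the visit as separate and Section 9.1.1 closes at the visit. If the lenient reading is intended, a sentence should say so.

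It can also be said that the scan is itself a contact. The imaging site has an investigator, effects such as heating or discomfort would mostly appear during the scan, and subjects may volunteer effects at any time. This stands and makes loss of information less likely. It does not supply a stated route to the eCRF.

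The visible schedule is incomplete. The MRI, adverse-event and follow-up-call rows are not shown, so the link between footnote 17 and Week 28 remains an inference.

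Four stronger readings are tempting, but the documents do not support them:
- *The events go wholly uncollected.* Section 9.2 has them reported and kept in source documents, and serious ones reach the sponsor.
- *An ADE rate per scan would be understated.* No such rate appears in the visible plan. AEs are tabulated as number and percentage of subjects, counted once per body system, and the three earlier scans are followed by scheduled visits.
- *About 10 final scans are affected.* That takes 7 of the 15 permitted day offsets times 22 patients (7/15 × 22 = 10.3). It needs scan days spread evenly, which nothing supports, and 22 patients, although SAP Section 1.4 says 40 mg will not be dosed. With the 12 completers planned for Cohort 1, the same arithmetic gives 7/15 × 12 = 5.6. Neither is an estimate.
- *Same-day scans share the gap.* A scan on the visit day can still be covered by that visit's questioning. The clear conflict concerns scans after the visit.

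**Conclusion.** The point holds in a limited form and is minor. When the Week 28 7T MRI follows the EOS visit, by up to 7 days, non-serious device effects are no longer sought at any scheduled visit. They depend on spontaneous reporting and have no defined path into the eCRF or the AE tables. The extent is indeterminate, from no final scans to all of them.

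This rests on three assumptions: footnote 17 is the Week 28 footnote; the AE end point in Section 9.1.1 also governs ADEs, since Section 9.2 gives no other; and the rows not shown add no later contact at which non-serious effects are sought. The point is worth making because the protocol names the device as an object of safety monitoring and the correction costs almost nothing.

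**What to change.** In Sections 9.1.1 and 9.2, state that AE and ADE collection ends at the later of the EOS visit and the final 7T MRI. Add to the planned 30-day safety call one non-directive question about adverse events and device effects up to that point, with answers entered in the eCRF, and align Section 7.1 and footnote 20 of Table 8-1 with this.

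The cost is a short protocol amendment, slightly later closure of the AE page, and one more question in a call that already takes place. No visit is added, and sample size and analysis are unchanged.

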## **9.2 Adverse device effects**

An adverse device effect (ADE) is an adverse event related to the use of a device. In this study, an ADE refers to the 7T MRI. This includes any adverse event resulting from insufficiencies or inadequacies in the instructions for use, the deployment, the implantation, the installation, the operation, or any malfunction of the device(s). This includes also any event that is a result of a use error or intentional misuse.

The occurrence of adverse device effects should be sought by non-directive questioning of the subject at each visit during the study. Adverse device effects also may be detected when they are volunteered by the subject during or between visits.

Adverse device effects must be recorded on the Adverse Event eCRF page under the signs, symptoms or diagnosis associated with them, accompanied by the following information:

1. the severity grade:
  - 1 (mild): usually transient in nature and generally not interfering with normal activities
  - 2 (moderate): sufficiently discomforting to interfere with normal activities
  - 3 (severe): prevents normal activities
2. its relationship to the device(s) in the comment section
3. its duration (start and end dates or if the event is ongoing an outcome of not recovered/not resolved must be reported)
4. if it constitutes a serious adverse device effect (SADE) the SADE Report Form in paper has to be completed

Once an adverse device effect is detected, it should be followed until its resolution or until it is judged to be permanent, and assessment should be made at each visit (or more frequently, if necessary) of any changes in severity, the suspected relationship to the medicinal product or device(s), the interventions required to treat it, and the outcome.

Information about known side effects of the device(s) can be found in the Informed Consent form. This information will be included in the subject's informed consent and should be discussed with the subject during the study as needed.

The Investigator should also instruct each subject to report any new adverse event/adverse device effect (beyond the protocol observation period) that the subject, or the subject's personal physician, believes might reasonably be related to the device used. This information should be recorded in the Investigator's source documents; however, if the ADE meets the criteria of an SADE, it must be reported to Novartis.

## 9.3 Serious adverse events and serious adverse device effects

### 9.3.1 Definition of SAE

An SAE is defined as any adverse event (appearance of (or worsening of any pre-existing) undesirable sign(s), symptom(s) or medical conditions(s)) which meets any one of the following criteria:

- is fatal or life-threatening
- results in persistent or significant disability/incapacity
- constitutes a congenital anomaly/birth defect
- requires inpatient hospitalization or prolongation of existing hospitalization, unless hospitalization is for:
  - routine treatment or monitoring of the studied indication, not associated with any deterioration in condition
  - elective or pre-planned treatment for a pre-existing condition (that is unrelated to the indication under study and has not worsened since the start of study drug)
  - treatment on an emergency outpatient basis for an event not fulfilling any of the definitions of a SAE given above and not resulting in hospital admission
  - social reasons and respite care in the absence of any deterioration in the subject's general condition
- is medically significant, e.g. defined as an event that jeopardizes the subject or may require medical or surgical intervention.

All malignant neoplasms will be assessed as serious under "medically significant" if other seriousness criteria are not met.

Life-threatening in the context of a SAE refers to a reaction in which the subject was at risk of death at the time of the reaction; it does not refer to a reaction that hypothetically might have caused death if it were more severe (see Annex IV, ICH-E2D Guideline).

Medical and scientific judgment should be exercised in deciding whether other situations should be considered serious reactions, such as important medical events that might not be immediately life threatening or result in death or hospitalization but might jeopardize the subject or might require intervention to prevent one of the other outcomes listed above. Examples of such events are intensive treatment in an emergency room or at home for allergic bronchospasm, blood dyscrasias or convulsions that do not result in hospitalization or development of dependency or abuse (see Annex IV, ICH-E2D Guideline).

Any suspected transmission via a medicinal product of an infectious agent is also considered a serious adverse reaction.

All AEs (serious and non-serious) are captured on the CRF; SAEs also require individual reporting to Novartis Chief Medical Office & Patient Safety (CMO&PS) as per [Section 9.3.2](#).

### **9.3.2 SAE reporting**

To ensure subject safety, every SAE, regardless of causality, occurring after the subject has provided informed consent and until 30 days after the last study visit must be reported to Novartis within 24 hours of learning of its occurrence as described below. Any SAEs experienced after this period should only be reported to Novartis if the investigator suspects a causal relationship to study treatment.

Note: SAEs reported by subjects deemed to be screen failures must be reported to Novartis as outlined here with appropriate information also captured in the CRFs as specified in the Site Operations Manual.

All follow-up information for the SAE including information on complications, progression of the initial SAE and recurrent episodes must be reported as follow-up to the original episode within 24 hours of the investigator receiving the follow-up information. An SAE occurring at a different time interval or otherwise considered completely unrelated to a previously reported one must be reported separately as a new event.

Follow-up information provided must describe whether the event has resolved or continues, if and how it was treated, whether the blind was broken or not (if applicable) and whether the subject continued or withdrew from study participation. Each re-occurrence, complication, or progression of the original event must be reported as a follow-up to that event regardless of when it occurs.

If the SAE is not previously documented in the Investigator's Brochure or Package Insert (new occurrence) and is thought to be related to the study treatment a CMO&PS associate may urgently require further information from the investigator for Health Authority reporting. Novartis may need to issue an Investigator Notification (IN) to inform all investigators involved in any study with the same study treatment that this SAE has been reported. Suspected Unexpected Serious Adverse Reactions (SUSARs) will be collected and reported to the competent authorities and relevant ethics committees in accordance with EU Guidance 2011/C 172/01 or as per national regulatory requirements in participating countries.

Follow the detailed instructions outlined in the Site Operations Manual regarding the submission process for reporting SAEs to Novartis. Note: SAEs must be reported to Novartis within 24 hours of the investigator learning of its occurrence/receiving follow-up information.

